**Rationale and Background:**

Dual antiplatelet therapy (DAPT) with aspirin and clopidogrel represents the standard of care for the prevention of recurrent ischemic events in patients undergoing percutaneous coronary intervention (PCI). For more than 20 years, dual antiplatelet therapy with aspirin and Clopidogrel has remained the cornerstone of treatment for patients with acute coronary syndrome (ACS). However, some patients have impaired clopidogrel response and thus persist with high on-treatment platelet reactivity (HPR) resulting in an increased risk of atherothrombotic events. The boxed warning added to the clopidogrel label underscoring the potential risk of adverse cardiovascular outcomes among patients with a “poor metabolizer” genotype and advocating the use of other antiplatelet medications or alternative dosing strategies for these patients has led to investigations of treatment options associated with more optimal platelet inhibition. These include switching to a novel generation P2Y12 inhibitor (e.g. prasugrel or ticagrelor).

Sodium GLucose Transport 2 inhibitors (SGLT2I), including dapagliflozin, reduce the likelihood of hospitalization for heart failure and death in persons with type 2 diabetes, of which the mechanism has not been fully elucidated. The mechanical effects of dapagliflozin on platelet function profiles have not yet been ascertained. It remains unclear if this reduction in cardiovascular death is mediated by decreased platelet reactivity.

**Hypothesis:**

1. Dapagliflozin attenuates platelet reactivity in patients with diabetes mellitus.
2. Dapagliflozin decreases platelet reactivity by 10%.

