***Null Hypothesis:***

There is no difference in response in patients with stable coronary artery disease on DAPT concerning PRUs on dapagliflozin.

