**Data Management and Statistical Analysis:**

The patient information will be initially recorded on CRFs which will be stored in the Adult Medicine Unit locking file cabinets, located at the Department of Clinical Medical Sciences, University of the West Indies, St. Augustine. Data will be coded per patient by first letter of first name, first letter of last name followed by numerical date of birth in the order of day, month, and year in a password-protected and encrypted database program in the office of Lecturer [name] at the Department of Clinical Medicine office, [name], Eric Williams Medical Sciences Complex. Each CRF and study database will be reviewed by 2 CRAs to minimize error, and clean and reconcile any conflicting data. We will aim for  $n$  of least 16 patient profiles, see sample size calculations. Any missing information will be censored and thus, not imputed. The study biostatistician will perform routine statistical analyses with SPSS v. 11.0 software (SPSS, Chicago, IL). Continuous variables are expressed as means  $\pm$  SD. Categorical variables are to be expressed as frequencies and percentages. Student's t-test will be used to compare continuous variables. Comparisons between categorical variables will be performed using the two-tailed Fisher's exact test or the Pearson's  $\chi^2$  test, as appropriate. A p-value of  $< 0.05$  will be considered statistically significant. No adjustments for multiple comparisons will be made. Results will be reported as least-square mean  $\pm$  SEM for the detailed analyses.

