**Sample Size Calculation:**

Assuming:

1. A 75 mg/d clopidogrel maintenance dose required at least 5 days and a 600 mg loading dose of clopidogrel required up to 8 hours to achieve  $\sim 50\%$  steady state of inhibition of ADP-induced platelet aggregation.
2. An estimated decrease of 10%, thus achieving a steady state inhibition of ADP-induced aggregation of 55% in patients with dapagliflozin.
3. Type 1 error rate 5%
4. Statistical power of 80%

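### The 10% decrease is listed as a hypothesis, but the plan tests only against no difference and specifies no confidence interval, so it cannot decide that hypothesis

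*Combined protocol and SAP*

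**What the plan says.** The Hypothesis section lists two statements. The first is directional: "Dapagliflozin attenuates platelet reactivity in patients with diabetes mellitus". The second gives a size: "Dapagliflozin decreases platelet reactivity by 10" percent. It does not say whether the 10% is relative or absolute, or whether it is measured against baseline or against the comparator group.

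The Null Hypothesis section gives a single null: "There is no difference in response in patients with stable coronary artery disease on DAPT concerning PRUs on dapagliflozin".

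Data Management and Statistical Analysis provides the test, "Student's t-test will be used to compare continuous variables", with significance at p < 0.05. The reporting format is "Results will be reported as least-square mean" with its SEM; means ± SD are used for description. Fisher's exact and chi-square tests are named for categorical variables. The section contains no confidence interval, margin or shifted null.

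The 10% appears once more, in Sample Size Calculation, as "An estimated decrease of 10" percent. There it is tied to inhibition of ADP-induced aggregation going from about 50% to 55%.

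**The concern.** A hypothesis that names a size needs an estimate, an interval and a rule for reading the interval against that size. The plan provides a test of zero and a standard error for each mean. Rejecting zero shows that some effect exists, not that it is 10%. Failing to reject zero does not show that the effect is below 10%. One of the two stated hypotheses therefore has no route to a decision.

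This matters because the only objective is descriptive, which calls for an estimate with its uncertainty. The Expected Outcomes section also looks to these results to inform regulators about a national medication programme. A bare p-value would be a weak basis for a statement about 10% in either direction.

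**Working it through.** **Hypotheses against analysis.**

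| Item | What it addresses | Speaks to 10%? |
|---|---|---|
| Hypothesis 1 | direction only | no |
| Hypothesis 2 | a 10% decrease | yes |
| Null hypothesis | difference = 0 | no |
| t-test, p < 0.05 | difference = 0 | no |
| Least-square mean ± SEM | precision of a mean | no |
| Sample size section | 10% as planning effect | assumption only |

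Mean ± 1 SEM covers an arm's own mean only about 65% to 67% of the time with 8 to 25 patients per arm. It is not an interval for the difference.

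**The plan's own figure.** The inputs are 50% versus 55% inhibition (5 points, or 5/50 = 10% relative), "Type 1 error rate 5" percent, 80% power and n = 25. No SD is given, so n = 25 cannot be reproduced. It can only be inverted for the SD it would need, assuming 1:1 allocation and a two-sided test, neither of which is stated:

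SD = 5 / [(1.96 + 0.84) × √(2/n per arm)]

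- 25 in total (12.5 per arm): 4.46 points; 4.27 from the noncentral t.
- 25 per arm: 6.31 points; 6.18 from the noncentral t.

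**Illustration, taking the 80% power as true.** This also assumes that the power carries over from inhibition to PRU.

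- Smallest significant effect as a share of the target: 1.96 / (1.96 + 0.84) = 0.70.
- t-based, 13 versus 12: SE = 4.27 × √(1/13 + 1/12) = 1.71 points. With t(23) = 2.069 the 95% half-width is 3.54 points. 3.54/5 = 0.71 of the target, or 7.1% relative.
- An observed 5 points has a 95% CI of 1.5 to 8.5 points (2.9% to 17.1% relative).
- The lower limit reaches 5 points only if the observed difference is about 8.5 or more.
- Observed differences of about 1.5 to 3.5 points are non-significant, yet their CI still contains the full 5 points.
- Power at half the target: 1 − Φ(1.96 − 0.5 × 2.80) = 1 − Φ(0.56) = 0.29.

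If 80% power instead held at 8 versus 8 or 25 versus 25, the half-width would be 3.56 or 3.52 points. The ratios come from the 80% power, not from this trial's size.

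**If the 80% power does not hold.** The SDs below are assumptions, in points of inhibition. Entries are power for a true 5-point effect, two-sided.

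| SD | 16 in total | 25 in total | 25 per arm |
|---|---|---|---|
| 5 | 46% | 67% | 93% |
| 10 | 15% | 22% | 41% |
| 15 | 9% | 12% | 21% |
| 20 | 7% | 9% | 14% |

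At SD 10 the 95% half-widths are 10.7, 8.3 and 5.7 points, each wider than the 5-point target. If the SD were 4.27 and only the 16 patients mentioned in the analysis section were enrolled, the half-width would be 2.145 × 4.27 × √(2/8) = 4.6 points (9.2% relative).

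**The case against.** Naming the planning effect as the alternative hypothesis is ordinary practice. There is one null, the objective is descriptive, and the Expected Outcomes section also mentions hypothesis generation. That stands, and it is why the remedy is to relabel the 10% rather than to build a test around it. It does not supply the missing interval.

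A t-test already yields a mean difference and its SE. From unadjusted arm means and SEMs a reader could form an approximate CI using √(SEM_A² + SEM_B²). That stands too: the gap is in prespecified reporting and interpretation, not in the data.

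The illustrative figures hold for any trial with 80% power and show nothing peculiar to this one. That also stands; they show only why a p-value cannot decide a hypothesis about size.

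Three stronger readings are tempting, and the documents do not support them:

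- That the sponsor intends to read p < 0.05 as confirming 10%, or p ≥ 0.05 as no effect. No section says so; it is a risk left open.
- That the 7% is in percentage points of inhibition. It is relative; on the sizing scale it is 3.5 points, with an SE of about 1.7.
- That this shows the sample size is wrong, or gives the trial's real precision. Without an SD, and with n = 25 not identified as total or per arm, neither can be established.

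**Conclusion.** The point holds as one of reporting and interpretation. Hypothesis 2 states a 10% decrease, the plan tests only zero, and no between-arm confidence interval or rule for 10% is specified, so the hypothesis cannot be decided as written. This conclusion rests on the text alone.

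The numerical size is conditional on the stated 80% power, a two-sided 5% test, 1:1 allocation and carry-over from inhibition to PRU. Precision is worse if the SD is larger than the sample size implies or if only 16 patients are enrolled.

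The change is worth making because it costs almost nothing. Its benefit depends partly on the scale of the 10% being settled, since without that there is no defined value to hold the interval against.

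**What to change.** In Data Management and Statistical Analysis, replace the mean ± SEM reporting with the following:

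- The main result is the group B minus group A difference in PRU at week 2, with a two-sided 95% CI, preferably adjusted for the baseline PRU already collected. The least-square mean wording suggests that a model was in mind; name it. An analysis of covariance with baseline PRU would give both the adjusted means and the interval.
- Express the difference and its limits also as a percentage of the group A mean. Dividing the limits by that mean treats it as fixed, so describe the percentage interval as approximate.
- Hypothesis 1 is supported if the CI excludes 0 in the direction of lower PRU.
- State in every case whether the CI includes a 10% decrease. A CI that includes both 0 and 10% is inconclusive. One that includes 0 but excludes 10% is evidence against a 10% decrease. One that excludes 0 but includes 10% supports a decrease and is compatible with 10% without establishing it.

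In Hypothesis, relabel 10% as the effect assumed for sizing. State its scale (relative PRU or points of inhibition) so that it agrees with Sample Size Calculation, where a rise in inhibition from 50% to 55% is called a decrease.

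The cost is a few sentences, with no new patients, samples or tests. The small downside is that the trial will probably have to report that a 10% decrease is not established.

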***Null Hypothesis:***

There is no difference in response in patients with stable coronary artery disease on DAPT concerning PRUs on dapagliflozin.

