**Study Goals and Objectives:**

1. To describe platelet function profiles of patients with stable coronary artery disease on DAPT on dapagliflozin.

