**Study Design:**

The study will be of a prospective, randomized, parallel trial design over 2 years. Patients at the Eric Williams Medical Sciences Complex (EWMSC), Mt. Hope, Trinidad and Tobago will be screened for potential eligibility.

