#### *Patient Interview and Case Report Form*

If a patient satisfies the selection criteria from the initial screening process, a physician or CRA-directed interview will then be administered. Demographic and anthropometric data will be recorded on a case report form (CRF). This will comprise the patient's medical and procedural history including any active medications.

Each patient will then be allocated via a computerized randomization program. Patients on DAPT for at least 6 months will be tested for platelet function testing with the P2Y12 VerifyNow assay at baseline. The patients will then undergo at least a 2-week course of dapagliflozin 10mg, followed thereafter by platelet function testing. The study will be randomized via a computer randomization program with a permuted block design and concealment allocation. It is also a controlled, prospective trial design, as group A serves to act as a baseline comparator group and group B has the desired antiplatelet strategy to be investigated over the longitudinal 2-week period. The study will also be blinded as patients will be unaware of their treatment assignments as well as the CRA or physician (Interventional Cardiologist) that performs the platelet function testing.

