#### *Blood Sampling, Phlebotomy*

Blood samples for platelet function testing will be collected at baseline before the patients are administered dapagliflozin (baseline sample). Blood will be drawn via an antecubital vein using a 21-gauge needle. The initial 5 mL of all blood samples will be discarded as medical waste as per the institution's policy (to avoid spontaneous platelet activation). Several laboratory tests will be performed including:

1. Complete Blood Count
2. Renal Function Profile
3. Hepatic Function Profile
4. VerifyNow P2Y12 PRU test assay - which will also be performed at the 2nd-week time point after patients have completed their assigned treatment schedules.

Overall, there will be 2 separate instances in which blood sampling/phlebotomy will be performed.

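### The null hypothesis, objective and 10% hypothesis name no comparator, and the analysis section does not say whether the within-B change or the randomised B-versus-A difference decides the trial

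*Combined protocol and SAP*

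**What the plan says.** All references are to the combined protocol and SAP.

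**Text written for one arm**
- Null Hypothesis: "There is no difference in response in patients with stable coronary artery disease on DAPT concerning PRUs on dapagliflozin".
- Study Goals and Objectives: "To describe platelet function profiles of patients with stable coronary artery disease on DAPT on dapagliflozin".
- Hypothesis, item 2: "Dapagliflozin decreases platelet reactivity by 10" per cent. It does not say whether this is relative to baseline or to group A.
- Patient Interview and Case Report Form: "The patients will then undergo at least a 2-week course of dapagliflozin 10mg, followed thereafter by platelet function testing". No group is named.

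**Text that sets up two arms**
- Study Design: "The study will be of a prospective, randomized, parallel trial design over 2 years".
- Patient Interview and Case Report Form: "group A serves to act as a baseline comparator group and group B has the desired antiplatelet strategy to be investigated". The same section specifies permuted blocks, concealed allocation and blinding, and calls the trial controlled.
- Sample Size Calculation: the link under n = 25 goes to a calculator for parallel designs.

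**Analysis text**
- Blood Sampling, Phlebotomy: "Overall, there will be 2 separate instances in which blood sampling/phlebotomy will be performed". These are baseline and week 2, so both contrasts can be computed.
- Data Management and Statistical Analysis: Student's t-test for continuous variables at p < 0.05, then "No adjustments for multiple comparisons will be made". The section does not name the arms, a primary contrast, or a paired or unpaired form.

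**The concern.** With PRU measured twice in two randomised groups, at least two contrasts fit the stated null: (i) the baseline to week-2 change within group B, and (ii) group B versus group A. An analyst who follows the null as written could run (i) and claim to be following the plan.

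Contrast (i) does not use the control group. It picks up anything that shifts PRU in both arms between the two visits, for example better clopidogrel intake after enrolment, an effect of repeat testing, or a change of assay lot. Group A is there to remove such effects. If the choice stays open, an uncontrolled fall can be reported as a dapagliflozin effect although the randomised comparison does not show one. If both are tested and either may be claimed, the stated 5% type 1 error no longer holds. The Expected Outcomes section foresees the result informing the Ministry of Health on a national drug programme, so the deciding test should be clear beforehand.

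**Working it through.** **1. Does the sample size show which contrast was meant?** Inputs from Sample Size Calculation: 50% versus 55% inhibition (5 points), type 1 error 5%, power 80%, n = 25. No SD is given, so n = 25 cannot be reproduced. Solving backwards, two-sided, with (1.960 + 0.842)² = 7.85:
- Two arms, 25 in total: SD = 5 × √(12.5 / (2 × 7.85)) = 4.46.
- Two arms, 25 each: SD = 5 × √(25 / (2 × 7.85)) = 6.31.
- Paired, 25 patients: SD of differences = 5 × √(25 / 7.85) = 8.92.

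Each reading fits some SD, so the number does not settle the contrast. The Budget lists 25 consent and case report forms, which suggests 25 in total; I use 12 in A and 13 in B.

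**2. False-positive rate if either contrast may be claimed.** Assumptions: normal PRU with SD 1 in both arms, no drug effect, no drift, two-sided 0.05, baseline to week-2 correlation ρ of 0.5-0.8. The documents give no ρ, and state sidedness only for Fisher's test.
- Two independent tests would give 1 − 0.95² = 9.75%.
- With equal arms, the within-B contrast and the between-arm difference in change correlate at 1/√2 = 0.71.
- With the between-arm difference in week-2 values, the correlation is √(1 − ρ)/2, which is 0.35, 0.27 and 0.22 at ρ = 0.5, 0.7 and 0.8.

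Simulation (40,000 trials per setting; 8+8, 12+13 and 25+25 patients) gives an either-test rate of about 8.3-8.5% using change and 9.3-9.9% using week-2 values. Each test alone is at about 5%.

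**3. A fall shared by both arms, no drug effect, 12+13.** For a fall of d SD, the paired t-test in group B has 12 degrees of freedom and non-centrality d × √13 / √(2(1 − ρ)).

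| Assumed fall | ρ | Non-centrality | Within-B test significant |
|---|---|---|---|
| 0.1 SD | 0.5 | 0.36 | 6% |
| 0.1 SD | 0.7 | 0.47 | 7% |
| 0.1 SD | 0.8 | 0.57 | 8% |
| 0.25 SD | 0.5 | 0.90 | 13% |
| 0.25 SD | 0.7 | 1.16 | 19% |
| 0.25 SD | 0.8 | 1.43 | 26% |

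The shared fall cancels in B minus A. The simulated between-arm rate stays at about 5% throughout.

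**4. Which between-arm test?** Take 12+13 and the back-solved SD of 4.46, so the planned effect is 5/4.46 = 1.12 SD. An unadjusted t-test on week-2 values has about 77% power at every ρ. Adjusting for baseline multiplies the SD by √(1 − ρ²), giving 3.86, 3.19 and 2.68 at ρ = 0.5, 0.7 and 0.8. Power rises to about 86% at ρ = 0.5 and 99% at ρ = 0.8. These figures carry the planned standardised effect over to PRU, which is an assumption.

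**The case against.** The strongest reply is that the document as a whole points to B versus A. Study Design, Patient Interview and Case Report Form and the calculator link describe a randomised, controlled, parallel trial, and in that setting the null most naturally means a difference between groups. No section mentions a paired test, and no section says that either contrast may be claimed. This stands to the extent that the comparator is missing from the hypotheses, objective and analysis text, not from the whole plan. It does not remove the point, because an implied design is not a pre-specified contrast and the Patient Interview section also describes a before-after sequence. The mention of least-squares means in the analysis section hints at a model but specifies none.

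Three stronger readings are tempting and are not supported:
- **That the two tests would contradict each other in direction.** What is shown is that one can be significant and the other not.
- **That the within-B test would usually mislead.** An assumed shared fall of 0.5 SD gives 38-74% at 12+13, but the documents give no drift, and patients already on DAPT for at least 6 months give no reason to expect one that large. The 0.1 SD rows show how modest the excess is if drift is small.
- **That the plan adopts a claim-either rule.** It does not. The 8-10% applies only if the open choice is used in that way.

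One point of language also stands: if PRU really falls in both arms, rejecting a before-after null is correct. The error lies in attributing the fall to dapagliflozin.

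**Conclusion.** The concern holds as a mismatch between hypotheses and design. The claims are written without a comparator, the trial randomises one, and the analysis section does not say which contrast decides.

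The figure least dependent on assumptions is the either-test false-positive rate of about 8-10% against the stated 5%. It assumes no drift, correlation 0.5-0.8, and that both contrasts are tested and either may be claimed. The rates of 6-8% and 13-26% also assume a shared fall of 0.1 or 0.25 SD at 12+13 patients. One pre-specified between-arm test holds about 5% in all these settings.

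This should be corrected before data lock. It does not undermine the design, which already contains the right comparison.

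**What to change.** 1. **Null Hypothesis, Hypothesis and Study Goals and Objectives:** restate each as group B versus group A. For example, the null becomes: mean week-2 PRU, adjusted for baseline PRU, does not differ between group B and group A. State the 10% decrease as relative to group A.
2. **Data Management and Statistical Analysis:** name one confirmatory test at two-sided 0.05, the between-arm difference in week-2 PRU adjusted for baseline PRU (ANCOVA). A null on unadjusted week-2 PRU would fix the contrast but give up the power shown in step 4 of the working.
3. **Same section:** state that within-arm changes are descriptive (mean change with 95% CI, no p-value) and cannot support a claim of effect.
4. **Patient Interview and Case Report Form:** reconcile the sentence that has the patients as a whole taking dapagliflozin with the existence of comparator group A. No section says what group A receives, so a B-versus-A null is incomplete until this is settled.

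Cost: wording only. Baseline and week-2 PRU are already collected, so no patients, samples or assays are added. The downside is that the within-arm result can no longer be claimed as evidence of effect.

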**Study Goals and Objectives:**

1. To describe platelet function profiles of patients with stable coronary artery disease on DAPT on dapagliflozin.

**Study Design:**

The study will be of a prospective, randomized, parallel trial design over 2 years. Patients at the Eric Williams Medical Sciences Complex (EWMSC), Mt. Hope, Trinidad and Tobago will be screened for potential eligibility.

